Sample Size and Power Calculations: A two sample T-test with a sample size 125 subjects per group (250 total) could detect an effect equal to 42% of the standard deviation with 90% power and an alpha level of 0.05. For the cost per month model with longitudinal data, if the contrast is the difference in mean total cost between treatment groups after 6 months of follow up, then a sample size of 125 per group (250 total) would achieve

90% power for an effect of 1.75 sd*months (0.29 sd on average) and an alpha level of 0.05. Here sd is in cost per month. If the contrast is the difference in mean total cost between treatment groups after 12 months of follow-up time, then an effect size of 3 sd*months (0.25 sd on average). The power calculations assume a compound symmetric covariance structure with a correlation of 0.5 for repeated measures on a patient.

For a binary outcomes, the following arrangements achieve 90% power with an alpha level of 0.05 and a sample size of 125 per group (250 total): 26% for the control group and 10% for the treatment group, a difference of 0.16 and an odds ratio of 0.316; 50% for the control group and 30% for the treatment group, a difference of 0.2 and an odds ratio of 0.429. For a Poisson count outcome, if the control rate is 0.5 per person year, and the exposure time is one year, then a sample size of 125 per group (250 total) would achieve 90% power with a rate ratio of 0.53 and an alpha level of 0.05.

Aim 3: Identify opportunities to optimize outpatient palliative care by: a) describing PD patient and caregiver characteristics associated with intervention benefits; and b) through direct patient and caregiver interviews.

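### The Poisson example in Aim 2 overstates its power: the stated inputs give about 86% for a two-sided 5% comparison, not 90%

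*Combined protocol and SAP*

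**What the plan says.** The sample size paragraph of Aim 2 gives one worked example for counts. Its claim is that "a sample size of 125 per group (250 total) would achieve 90% power with a rate ratio of 0.53 and an alpha level", with alpha set at 5%. The claim is conditional on two assumptions about the events, introduced by the words "if the control rate is 0.5 per person year, and the exposure time is one year". The example names no formula or test, does not say whether alpha is one- or two-sided, does not mention over-dispersion, and is not tied to a particular outcome.

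The Statistical Analyses section of Aim 2 assigns Poisson regression to count outcomes. It lists hospitalisations and emergency room visits, together with nursing home placement, in the primary service utilisation comparison. The figure of 125 per group comes from the Aim 1 sample size section: 150 randomised per group less up to 25 dropouts by month 6.

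**The concern.** The example supplies every input that a power calculation for two Poisson rates needs, so it can be checked directly. The usual two-sided calculations fall short of 90% by roughly three to six points. If the stated figure is too high, a reader would take the chance of missing a rate ratio of 0.53 to be 10% when it is about 14%, and would take 0.53 to be the ratio detectable with 90% power when a larger reduction is needed. No other power statement in the plan addresses counts, so nothing else corrects the impression.

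**Working it through.** **Inputs** (Aim 2 sample size paragraph): 125 per group, control rate 0.5 per person-year, one year of exposure, rate ratio 0.53, alpha 0.05. Allocation is 1:1 (Aim 1, Randomization). No over-dispersion is stated, so none is assumed.

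**Sidedness.** This is not stated. Two-sided is inferred from the neighbouring figures. The binary examples in the same paragraph (26% against 10%, and 50% against 30%, 125 per group) give 91.3% and 90.2% two-sided, but 95.4% and 94.7% one-sided. The two-sample comparison at 0.42 SD with 125 per group gives about 91% two-sided.

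**Expected events.** Control: 125 × 0.5 × 1 = 62.5. Intervention: 62.5 × 0.53 = 33.125. Total: 95.625.

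**Common quantities.** |ln 0.53| = 0.6349. Standard error of the log rate ratio under the alternative: √(1/62.5 + 1/33.125) = √0.04619 = 0.2149.

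**Reproducing the plan's figure.** Take the null variance at the control rate in both arms, as a recognised sample-size formula for Poisson regression with a binary covariate does:

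- Null standard error: √(2/62.5) = 0.1789.
- Power = Φ((0.6349 − 1.96 × 0.1789) / 0.2149) = Φ(1.323) = 90.7%.
- At 125 per group this formula gives 90% at a rate ratio of 0.535, so 0.53 is a natural two-decimal result from it.

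**Other two-sided approximations.**

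- Wald on the log rate ratio: Φ(0.6349/0.2149 − 1.96) = Φ(0.994) = 84.0%.
- Log rate ratio with pooled null variance (mean count 47.81): Φ((0.6349 − 1.96 × √(2/47.81)) / 0.2149) = Φ(1.089) = 86.2%.
- Score test on the difference: Φ((62.5 − 33.125)/√95.625 − 1.96) = Φ(1.044) = 85.2%.
- Square-root transform: Φ(2(√62.5 − √33.125)/√2 − 1.96) = 86.0%.
- Schoenfeld's formula on 95.6 events: 87.4%.

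The first formula differs because its null standard error is 0.1789, whereas the pooled value is √(2/47.81) = 0.2045. When the intervention rate is about half the control rate, setting both arms at the control rate makes the null variance too small and the power too high.

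**Enumeration.** Summing over all pairs of Poisson totals avoids the approximations:

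| Test, two-sided 5% | Rate ratio 0.53 | 0.51 | 0.50 |
|---|---|---|---|
| Wald | 85.5% | 88.8% | 90.2% |
| Score | 86.0% | 89.2% | 90.6% |
| Likelihood ratio | 86.0% | 89.2% | 90.6% |
| Exact conditional | 83.5% | 87.0% | 88.6% |

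At a rate ratio of 1, the rejection probability in one tail is 2.4% (Wald), 2.5% (score), 2.5% (likelihood ratio) and 2.0% (exact conditional). The first three tests therefore hold their nominal level closely, and the 86% is not the product of a conservative test.

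**The case against.** The best defence is that 90% can be reproduced from the plan's own inputs, two-sided, with a recognised formula for the analysis that the plan names. That is true, and it rules out a reading that the heading might invite, namely that the authors made an arithmetic error. The documents are consistent with a correctly executed approximation. But reproducing a figure shows only where it may have come from. Power is the probability that the planned test rejects, and for Poisson regression with these inputs that is about 86%.

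A second defence is that the example is illustrative. Its control rate is hypothetical, it is attached to no named outcome, and the same paragraph also gives power for binary outcomes. This stands, and it limits the importance of the point.

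A third is that the answer depends on the test, from 83.5% to 86.0% by enumeration and 84.0% by the closed-form Wald calculation. This also stands, and it is why the restated figure should name the test. None of these values reaches 90%.

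**Conclusion.** The stated power is about four points too high: about 86% at a rate ratio of 0.53, with 90% reached at about 0.50. This assumes a two-sided 5% Wald or score comparison, 125 participants per group each contributing a full year, and Poisson variation without over-dispersion. Over-dispersion, or loss after month 6, would lower the power further; neither is quantified here. The point is minor.

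Three stronger readings are tempting and are not supported:

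- **That a one-sided test was used.** A one-sided 5% calculation also lands near 90%. But a two-sided formula already explains the figure, and the neighbouring examples fit two-sided alpha.
- **That the real horizon is six months, so power is far lower.** The six-month horizon in Aim 2 belongs to the cost comparison. The count example states one year of exposure, which matches 12 months of follow-up with utilisation collected every six weeks, and the utilisation comparison carries no six-month limit.
- **That the trial is underpowered.** The example does not set the sample size and has no bearing on the primary outcomes, QOL-AD and ZBI.

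**What to change.** Replace the power statement for the Poisson example in the Aim 2 sample size paragraph with wording such as:

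> *About 86% power at a rate ratio of 0.53, or 90% power at a rate ratio of about 0.50 (two-sided alpha 0.05, Wald or score test, one year of exposure per participant, no over-dispersion).*

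The control rate and the group size stay as they are. The cost is a text correction that makes the stated figure slightly less favourable. The sample size, endpoints and analyses do not change.

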* administered by clinician – inclusion/exclusion form, NAT – PD, MOCA, MDS UPDRS Motor Subscale, Hoehn and Yahr Staging, History, UK Brain Bank Clinical Staging, Patient Performance Scale and Charlson Comorbidity Index

ΩΩ administered by coordinator – consent, UBACC, QOL – AD, PROMIS – 29, Medications, Demographics and Health Utilization

ü self-administered (patient) - PDQ – 39, ESAS –PD, FACIT – SF, PG -12 and PROMIS -29

β self- administered (caregiver) - Zarit Burden of Care Instrument, EQ-5D

After review of consent with subject, UBACC then should be administered next by the coordinator to see if subject has the capacity to consent prior to signing consent.

No study procedures should be completed prior to the consent process.

QOL – AD and Zarit Burden of Care Instrument (ZBI) [care giver] if applicable, should be administered first prior to any other study procedures.

Please note, CGI will be administered by coordinator at 3 and 9 month visit (omit questions 2C at 3 and 9 month visits) and at 6 and 12 month visit it will be administered by the clinician.

6 week assessment after every scheduled visit will be done by phone.

3, 6, 9 and 12 month visit, only capture medication changes.

Data collection for all study visits can be done by phone, online survey, via telehealth, or in person.

Time windows for study visits and data collections are as follows:

- The 3, 6, 9, and 12-month visits should occur within +/- 4 weeks of scheduled date.
- The one week follow-up phone call should occur within 1 week of scheduled date.
- The six week follow-up phone call should occur within 2 weeks of scheduled date.
- The six-week health care utilization survey call should occur within 2 weeks of scheduled date.
